If the client has not disclosed to their partner and the client wants to seek conception, they will be linked to TASO's assisted disclosure program (including the option of home-based joint couples testing), as disclosure is key to acquiring partner cooperation with TUI/MSI. If the HIV status of the partner is negative or unknown, the client will be strongly encouraged to have their partner come in for HIV testing (though this is not required, unless the client is being screened for study participation), as the partner's HIV status informs the selection of the best SCM. The nurse will stress the importance of the partner attending SCC sessions and clients will be given a formal invitation letter to give to their partner to inform them of the value of SCC, how SCM reduces risk of transmission, and the importance of being HIV tested and participating in SCC. Invitation letters have been used successfully by TASO and others to engage male partners in PMTCT.⁶¹ Furthermore, home-based counseling will be offered if the partner cannot attend in person or over the phone, and the client reports difficulties with properly using SCM; this is a feasible and sustainable strategy at TASO, which has long offered home-based services as an option to the few clients who are unable to make it to the clinic. However, despite our recognition of the important role that both male and female partners play in childbearing decisions and the ability to use SCM, partners will not be required to attend SCC in order for clients to receive SCC. Our pilot showed that women have an especially hard time getting their uninfected partners to attend, and neither we nor TASO or the MoH are comfortable withholding SCC from these women who need the service. We do not know how effective SCC can be without both partners attending, even though several couples in the pilot were

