- * Discuss other risk reduction options: circumcision (if negative male; available at TASO); sperm washing (available for ~\$1000) and PrEP (available for ~\$120 monthly) are available by referral, but are cost prohibitive for nearly all.
- * Review with client/couple their action plan for the coming month prior to 2nd session.

Follow-up sessions (up to 5 sessions; scheduled after female's menstrual period each month til pregnancy; 20 min):

- * Ascertain how well the client/couple identified the timing of woman's ovulation and used selected SCM.
- * Assess whether calendar, SMS texts and tool kit were helpful; identify strategies to overcome barriers.
- * Assess infected partner's ART adherence and refer for adherence counseling if needed.
- * Use tracking form (see manual) to record success and challenges related to use of SCM.
- * If partner did not attend, and SCM was not used successfully, discuss with client strategies for engaging partner.
- * Pregnancy test if woman's period is skipped; if pregnant, HIV test the partner and start HIV+ mothers on PMTCT.
- * Partner HIV test is done at completion of intervention and again 3 months later to confirm.

If after 6 mos. of correct SCM use pregnancy has not been achieved, SCC is discontinued and the couple referred to fertility clinic for infertility tests. Guidelines call for waiting 12 mos., but they do not account for use of SCM to target the fertile period. Infertility tests (\$70) will be paid for by the study for research participants, so that we can collect data on infertility rates, which are unknown in this population; otherwise, clients will need to pay for these tests.

Arm 2: Training workshop for integration of SCC into FP (SCC2)

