This model for integrating SCC into existing FP services mimics the approach used by the MoH for infusing new services. Like SCC1, SCC2 will also use screening of childbearing desires and clients who report such desires will be encouraged to discuss this with their providers, and the triage station will record the information in the client's chart so that providers can refer the client to the FP nurses for SCC or contraception. Training of FP nurses (see Fig. 2) will be mostly educational and use role plays, but will not train on use of MI style communication with clients. A simplified manual and some (SCM instructional brochures, fertility calendar) but not all tools (instructional videos; SCM kits) produced for SCC1 will be used in SCC2. Supervision will not be provided by the study supervisors; rather, FP nurses may consult with clinic physicians and the FP clinic on the hospital campus when needed, which is the typical approach for new services. Like SCC1, SCC2 sessions will be recorded and a random selection coded for fidelity by the Project Director, but feedback will not be given to the nurses, as this is not the norm when new services are added. SCC2 is designed to reflect how new treatment advances are integrated into routine care by the MoH, and to represent a viable, less intensive alternative to the structured, multi-component SCC1, the comparison of which provides critical data to guide the MoH and other policy makers on how to best incorporate SCC into FP services. SCC sessions attended by participants will be logged and research participant surveys will assess SCC and FP services received.

Arm 3: Existing FP services (usual care control) Each study site currently provides FP services that focus on providing contraception and PMTCT care, but there's no SCC. The usual care sites will continue to provide FP services as is, with no use of routine screening of childbearing desires or SCC. Routine HIV and FP care in Uganda is unlikely to incorporate SCC during the course of this study, as SCC guidelines have been available

for years, yet SCC has remained scarce in Uganda and SSA. Also, TASO has indicated it has no plans to integrate SCC into usual care until the study ends and it sees efficacy and cost-effectiveness data.

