Routinely collected clinic data will be used to analyze FP services in the overall clinic population to examine clinic capacity and fidelity to the intervention. The triage book and childbearing screening item (in SCC1/SCC2 sites) will be used to determine: (a) # who do not want children and % receiving contraception services, and (b) # reporting childbearing desires. FP registries will indicate # new clients receiving FP services (not seen by FP in past year), and % of FP recipients using dual contraception. These will be tracked longitudinally to assess intervention effects on clinic level FP services. % of clients receiving FP referrals after triage will be compared across all 3 arms using research cohort data, since childbearing screening is not used at the usual care site.

Research Participants. The assigned FP programs at each study site will be implemented clinic-wide for all clinic clients, but the 66 study clients enrolled at each site will meet the following **eligibility criteria**:

1. Adults of reproductive age (men age 18-60; women age 18-45).
2. Considering childbearing with their spouse/partner. This will be determined via the triage screening item.
3. Reports having disclosed HIV status to partner. TASO counselors provide clients with assisted disclosure services to help them disclose to partners. Therefore, interested clients who have not yet disclosed their HIV status to their partner will be assisted to do so if they wish, after which they can be considered for enrollment.
4. Partner is HIV-negative. All couples can benefit from SCC and FP, but we focus on discordant couples due to the heightened value of SCC for reducing horizontal HIV transmission. We will use a rapid HIV test to confirm partner's status, and offer the option of a home-based test (a service offered by TASO) if necessary. Confirming the partner's status enables us to accurately assess intervention effects on seroconversion.

ART use is not an eligibility criterion, but SCC will be used to advise and support clients to start and adhere to ART before trying to conceive with SCM. TASO provides ART to all clients in serodiscordant relationships.

Note that only the HIV+ client will enroll in the study and participate in the survey research, not their partners.

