To assess correct SCM use, respondents will be asked if they used TUI, MSI, or sperm washing in the past 6 months and how often. Given the cost of sperm washing, TUI (applicable for all couples) and MSI (applicable for couples in which the male is HIV negative) are the two feasible methods for most clients. Clients will be asked in an open-ended format to describe exactly how they implemented the method. For each method, the interviewer will be looking for 3-5 pre-established pieces of information (e.g., identifying the timing of woman's fertile period; # of days in the fertile period; using condoms outside of the fertile period; collection of semen and insertion using syringe) from the participant's response, which will be used to rate the response as indicating "fully accurate" use of the method, "partially accurate" or no use. Only fully accurate use will be considered correct SCM use for the primary analysis, but the 3-level variable will be examined in secondary analysis. Social desirability may influence responses, but clients are not likely to be able to describe the method in such detail unless they are actually following the procedures. This assessment will occur prior to administering the SCM knowledge part of the survey (which uses a less detailed description of the method) to avoid biasing the measure of SCM use. We will ask about partner use of PrEP and male circumcision, but these methods will not be considered when rating proper SCM use since they are not specific to the context of conception.

Secondary outcomes: (1) achievement of desired pregnancy status and pregnancy outcome [live birth or miscarriage (we will not be able to adequately assess induced abortions due to strong stigma and illegality of such abortions, making it very difficult to get accurate data)] assessed via self-report and chart abstraction; (2) partner seroconversion, with HIV testing at month 12 in addition to testing as part of SCC); (3) PMTCT adherence (enrollment by 14 weeks gestation, ART use during pregnancy and post-delivery, infant ART

prophylaxis, and early infant diagnosis of HIV) for those who become pregnant, assessed via chart abstraction; (4) self-reported consistent condom use in past 6 months (generally for those not seeking childbearing, and all times outside of 3-day fertile period of each month for those seeking childbearing and using TUI/MSI).

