Aim 2: Assess intervention effect on secondary outcomes (pregnancy status; PMTCT use, consistent condom use, partner seroconversion): We will use the same analytic strategy as described for Aim 1.

Aim 3: Examine eIMB moderators and mediators of intervention effects on SCM and contraception use. We will identify bivariate correlates of the primary outcome from among baseline variables using correlation coefficients, t-tests and chi square tests, followed by a stepwise regression approach to identify a parsimonious list of predictors. We will then use longitudinal analyses to investigate changes in the primary outcome relative to changes in dependent variables such as SCM knowledge, motivation and self-efficacy. Like the baseline cross-sectional analysis described above, we will start with bivariate analyses that will inform a subsequent stepwise regression approach. We will use clinic fixed effects, because with only 9 clinics, clustering standard errors to correct for correlation between patients in the same clinic would significantly reduce power. Robust estimation techniques can adjust for correlation in multiple observations of a given patient over time. We will use a similar analytic approach to examine determinants of the secondary outcomes. Lastly, we will investigate the paths through which the intervention works, and subgroups that benefit more from the intervention. E.g., male clients and their partners may use contraception/SCM more because of their greater control over decision making and ability to secure partner participation in SCC. We can test this hypothesis by adding an interaction term between gender and the intervention. Using methods described by MacKinnon⁷⁶ and others,^{77,78} we will assess whether the intervention has a direct impact on contraception/SCM use or mostly though a mediating variable such as communication with provider about childbearing needs (which may result in clients being more apt to receive the information and encouragement needed to use SCM/contraception).^{46,79}

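### Partner seroconversion counts SCC-linked HIV tests on top of the month-12 test, so ascertainment is unequal between arms (a small bias against SCC), and the planned logistic model is fragile with so few events

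*Combined protocol and SAP*

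**What the plan says.** Under Measures, Secondary outcomes, the second outcome is "partner seroconversion, with HIV testing at month 12 in addition to testing as part of SCC". No arm restriction is placed on the month-12 test.

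The SCC-linked tests appear in the Arm 1 (SCC1) list of follow-up sessions: "if pregnant, HIV test the partner and start HIV+ mothers on PMTCT", and "Partner HIV test is done at completion of intervention and again 3 months later to confirm". The Arm 2 section gives no partner-test times. It says only that "A simplified manual and some (SCM instructional brochures, fertility calendar) but not all tools (instructional videos; SCM kits) produced for SCC1 will be used in" this arm. For Arm 3, "The usual care sites will continue to provide FP services as is, with no use of routine screening of childbearing desires or SCC", and no partner test is scheduled there between baseline and month 12.

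Under Research Participants, the partner's negative status is confirmed by rapid test at entry, with a home-based option. The same section adds: "Note that only the HIV+ client will enroll in the study and participate in the survey research, not their partners".

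For the analysis of secondary outcomes, Aim 2 says: "We will use the same analytic strategy as described for Aim 1". Aim 1 is a logistic regression with baseline covariates. The Data analysis section adds intent-to-treat, attrition weights and a sensitivity range of ICC values. Nothing states which partner tests count, in what window, or how a partner with an SCC test but no month-12 test is classified.

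**The concern.** An outcome compared between arms should be looked for equally hard in each. Here one source of positives exists only where the intervention is delivered. A partner infected early who has no month-12 test cannot be found in usual care but can be found through SCC. A positive from an SCC test after month 12 could also be counted, with no usual-care counterpart. Attrition weights do not settle this, because they address dropout and not unequal testing.

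The Recruitment section balances enrolment by sex partly so that effects on partner seroconversion can be examined, so an arm comparison is intended. Aim 4 also uses seroconversion status in its unit of effect.

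A second, separate matter is the model. Seroconversions are likely to be few, and maximum-likelihood logistic regression with several covariates behaves poorly with few events. If a compared group has none, the estimate is infinite.

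**Working it through.** The plan gives no incidence, expected event count or power for this outcome, so there is no stated figure to reproduce.

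**1. Unequal detection**

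Inputs:
- f, the share of partners with no month-12 test: 10%. This is the client attrition in the Power analysis, used as a proxy.
- g, the share of those partners who had an SCC test: assumed 0.25 to 0.8. The low end matches testing in SCC1 only and only among the half of clients whom the Power analysis expects to pursue pregnancy (0.5 × 0.5 = 0.25 of the combined SCC group).
- s, the share of 12-month infections present by the last SCC test: assumed 0.5 to 0.75 (constant hazard, last SCC test at about month 6 to 9).

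Share of infections found, at equal true risk:
- Usual care: 1 − f = 0.90.
- SCC: 1 − f + f·g·s.
- Ratio: 1 + f·g·s/(1 − f).

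Results at f = 0.10:
- g = 0.25, s = 0.5: 1 + 0.0125/0.90 = 1.01.
- g = 0.8, s = 0.75: 1 + 0.06/0.90 = 1.07.
- Ceiling, g = s = 1: 1/0.90 = 1.11.
- With no missing month-12 tests and no later tests counted, the ratio is 1.00, because a partner infected earlier still tests positive at month 12.

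Extra infections found among the 260 SCC partners are 260·r·f·g·s. At r = 1% and the low inputs this is 2.6 × 0.0125 = 0.03. At r = 3% and the high inputs it is 7.8 × 0.06 = 0.47.

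The ratio concerns infections found among everyone enrolled, with partners not found positive treated as uninfected. That is the setting in which the bias runs against SCC. The plan states no denominator. If early SCC negatives also entered as final outcomes, the observed-risk ratio would be (1 − f + f·g·s)/(1 − f + f·g). At g = 0.8 and s = 0.5 that is 0.94/0.98 = 0.96, a small shift the other way. This is a further reason to fix the rule.

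**2. Tests after month 12**

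Up to six monthly sessions plus 3 months ends at about month 9 to 10 if sessions start promptly. A later test needs a delayed start. The introductory consultation does provide for delaying pregnancy in some circumstances, so late tests are possible but not the default.

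**3. Sparse events**

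The Overview gives 130 clients per arm. With 10% loss, 117 remain in usual care and 234 in the combined SCC group, 351 in all. The risk r is assumed to be 1% to 3%, and clustering is ignored.
- Expected events: 351 × 0.01 = 3.5 to 351 × 0.03 = 10.5, or about 4 to 11.
- P(no events in n) = (1 − r)^n. For n = 117 this is 0.31, 0.09 and 0.03 at r = 1%, 2% and 3%. For n = 234 it is the square of these: 0.10, 0.01 and below 0.01.
- Either compared group empty, 1 − (1 − P₁₁₇)(1 − P₂₃₄): about 37%, 10% and 3%.
- At least one of three arms empty, 1 − (1 − P₁₁₇)³: about 67%, 26% and 8%.

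**The case against.** The strongest counter-argument is that the effect is small. The month-12 test does most of the work, and even the upper inputs above add less than half an infection to an outcome for which the plan claims no power. That stands. It limits the weight of the point, but it does not supply the missing rule.

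A reader might infer that far more than 10% of partners will miss month 12, because partners are not enrolled and the plan says that "women have an especially hard time getting their uninfected partners to attend". The documents do not support this. The remark concerns attendance at SCC sessions in the pilot, and only women's partners; the plan also says most female partners attended. Every enrolled client's partner was tested at entry, with a home option, so the sample is selected for partners who can be tested. Client attrition may still understate missing partner tests, but no higher figure is documented. Partners who are hard to reach at month 12 are also less likely to have had an SCC test, so g should fall as f rises.

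A reader might also infer that both SCC arms follow the same test schedule. It is written only for SCC1. What SCC2 does is not stated, which weakens the contrast with usual care and opens a possible imbalance between SCC1 and SCC2.

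An obvious remedy, counting only month-12 test results, could do harm. A partner already found positive through SCC may not be retested, and dropping that infection would favour SCC. This stands and shapes the fix.

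**Conclusion.** The point holds as a gap in the outcome definition with a modest effect. Followed as written, the plan ascertains partner infection unequally between SCC and usual care, and possibly between SCC1 and SCC2. At 10% missing the detection ratio is about 1.01 to 1.07, with a ceiling of 1.11. It is larger only if more partners miss month 12, for which the documents give no figure. With all enrolled partners as the denominator the bias runs against SCC, so it would not manufacture a benefit. The stronger reading, that it is likely to hide a real benefit or to suggest harm, is not supported at this size.

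The modelling point is separate and does not depend on the testing imbalance. It rests on the assumed 1% to 3% risk, 10% loss and independence between partners. On those terms an empty comparison group is a real possibility at the low end (37%) and unlikely at the high end (3%).

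**What to change.** Change the analysis-plan wording only; testing done for care stays as it is.

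- Define the comparative outcome as partner HIV status at the month-12 assessment, with the same window in all arms, among partners whose month-12 status is ascertained.
- Where the month-12 assessment takes place, carry an earlier documented positive forward as positive, so that a known infection is not lost for want of a retest.
- Exclude tests after the window from the comparison.
- Report month-12 ascertainment by arm, and tabulate SCC-triggered positives that have no month-12 assessment.
- Add a sensitivity analysis counting all documented infections by month 12.
- Analyse with Firth-penalised or exact logistic regression with arm only, give risk differences with intervals, and keep the plan's range of ICC values.

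Costs: a few infections detected only through SCC move from the main comparison to the sensitivity analysis, and covariate adjustment is given up for this outcome. Carrying forward positives leaves a small residual asymmetry where a partner would have missed the month-12 test anyway. The ascertainment table by arm shows how much room there is for it.

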STUDY PROTOCOL
May 1, 2017

Project Title: Integrating Safer Conception Counseling to Transform HIV Family Planning Services

NCT03167879

Registered on clinicaltrials.gov on 5/23/17

STUDY PROTOCOL

Overview. This 3-arm, cluster RCT will compare two models for implementing a comprehensive FP program that integrates SCC within current FP services in HIV clinics—an up to 6-session, multi-component, structured SCC intervention (SCC1), and a workshop to train FP providers on use of SCC guidelines (SCC2)—versus existing FP services (usual care). Both SCC1 and SCC2 will use routine screening for fertility desires and a workshop for training FP nurses to implement SCC, but SCC1 is differentiated by its use of a structured counseling SCC protocol and manual (as opposed to the clinical acumen of the trained FP nurses), and inclusion of client outreach and ongoing supervision support. Each arm will be implemented at 2 sites (6 sites in total) and each site will enroll 65 clients (total n=390) with serodiscordant partners who have childbearing desires at recruitment. Participants will be surveyed at baseline, months 6 and 12, and post-pregnancy for those who become pregnant prior to month 12. The primary outcome is correct use of SCM or contraception (depending on desired pregnancy status following SCC consult); secondary outcomes are pregnancy status, PMTCT use (if pregnant), partner seroconversion, and condom use. A cost-effectiveness analysis will also compare the 3 arms to inform policy and practice recommendations for settings of various resource levels.

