able to successfully use SCM when the partner did not attend. The proposed study will provide data to answer this important question. In our pilot, most female partners attended SCC, but if not, she will be given a referral (via the male client) to come to TASO or the hospital FP clinic for contraception if they decide against childbearing; or if seeking childbearing the male will be asked to report on the timing of his partner's fertile period with information from his partner, or the nurse will phone the partner for this information with consent from the male. After conception, the FP nurse will provide PMTCT services; if clients have a miscarriage, the cause will be addressed if possible, than contraception or further SCC offered, as desired.

SCC Introductory Consultation (45-60 minutes):

- * Build rapport and supportive environment; encourage client/couple to express needs and expectations.
- * Discuss context related to readiness for childbearing (partner HIV status; HIV disclosure; partner's fertility desire; # of existing children; health of relationship; available resources/supports; work patterns separating the couple).
- * Review HIV and health risks of childbearing for mother, infant, & partner, & factors that contribute to or protect from risk (SCM; ART; CD4; PMTCT; STIs; alcohol use; nutrition). Encourage delaying pregnancy if medical condition not optimal (not on ART > 6 mos.; CD4<200; active STI) and provide treatment (for STIs, acute OIs, or ART) as needed.
- * Encourage client/couple to consider this information and take time to decide whether or not they want to have a child, and return the next week for either SCC or contraception counseling and services accordingly.

SCC Session 1 (20-30 minutes):

- * Review client/couple's decision: if no longer desire a child, provide contraception; otherwise continue with SCC.
- * Teach client to time the woman's ovulation period and fertile window using pregnancy calendar.
- * Client/couple receives instruction on selected SCM (TUI, or MSI if female HIV+ and male HIV-). Brochures and tool kit specific to the chosen method (e.g., condoms, lube, syringe, plastic cup) are given to client to take home; instructional video will be shown; SMS texts will be used to remind client of start of fertile period if they have a phone.

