Recruitment. We will enroll 3-4 clients per month over 18 months at each site, which is feasible as >20 clients met this eligibility criteria in each recruitment month in our pilots. Recruitment will be stratified by sex to ensure a 50/50 gender balance, which will better enable us to examine intervention effects on partner seroconversion

and to gain the perspective of both male and female clients regarding fertility. We could enroll the sample more quickly, but the long enrollment period ensures we can recruit the target number of men, and enables us to have our 3 site coordinators manage three sites each (min. 1 day per week at each clinic) to limit personnel costs. Clients at the SCC1 and SCC2 sites who report at triage that they desire to have a child with a negative or unknown HIV status partner will be referred by triage to the site coordinator for screening. Screening (incl. partner HIV testing) and baseline survey will be completed prior to the initial SCC consultation. At the usual care site, the childbearing screening item will be included at triage only during the days of recruitment, which will be used to identify potential participants who will then be referred to the site coordinator for the same screening conducted at the intervention sites; the data from the screening item will not be placed in the client's chart or given to the FP nurse, as this screening is not part of usual care. Clients who decline to bring their partner in for HIV testing (but are otherwise eligible) and thus do not participate, will be asked to provide basic sociodemographic and partner characteristics in order to assess how they differ from the enrolled clients.

Data Collection

Assessment schedule: The baseline assessment will be done by the site coordinator once eligibility is confirmed, followed by assessments at months 6, 12, and post-pregnancy (if pregnancy occurs prior to month 12). To minimize attrition we will collect contact info (phone numbers and maps of homes), including contact information for family or friends who have frequent contact with the client. Clinic staff will also be able to help us track clients that we have difficulty reaching. In our current study we achieved 94% retention at Month 12.

Participant Compensation: Participants will receive 20,000 Ush (~\$6 USD) at each assessment.

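### PMTCT adherence is compared between arms only among clients who become pregnant, so a difference could reflect who conceived rather than better PMTCT care

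*Combined protocol and SAP*

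**What the plan says.** Measures, Secondary outcomes (3), defines PMTCT adherence through four components: enrolment by 14 weeks of gestation, ART during pregnancy and after delivery, infant prophylaxis, and early infant HIV diagnosis. It is measured "for those who become pregnant, assessed via chart abstraction". For all secondary outcomes, Data Analysis Plan, Aim 2, states: "We will use the same analytic strategy as described for Aim 1". Aim 1 is a logistic regression between arms with baseline covariates, of which childbearing stigma, age and sex are given as examples.

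SCC acts on who conceives and in what state of health. The SCC Introductory Consultation (Arm 1) instructs: "Encourage delaying pregnancy if medical condition not optimal (not on ART > 6 mos.; CD4<200; active STI". Research Participants adds that SCC supports clients to start and adhere to ART before they try to conceive. The Arm 1 text on structured sessions reports that many pilot clients decided against childbearing after the consult and discussion with their partner. Arm 3 (usual care) has neither SCC nor routine screening of childbearing desires.

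On the population, Recruitment says: "Recruitment will be stratified by sex to ensure a 50/50 gender balance". The fourth eligibility criterion is "Partner is HIV-negative", and Research Participants closes with: "Note that only the HIV+ client will enroll in the study and participate in the survey research, not their partners". Follow-up sessions (Arm 1) ties PMTCT to the mother's own infection: "start HIV+ mothers on PMTCT".

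**The concern.** Randomisation makes the arms comparable as enrolled. It does not make the pregnant women in one arm comparable with those in another when the intervention changes who becomes pregnant. Pregnancy status is itself a secondary outcome that SCC is meant to move.

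The link to this endpoint is direct. Women not established on ART are advised to delay, and ART use is part of the adherence definition. If some of them defer beyond follow-up, the women who conceive under SCC are more often already on ART. Their adherence then looks better even if PMTCT care is identical in all arms. CD4, active STI and changed decisions about childbearing are further routes by which the pregnant groups could differ.

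At stake is what Aim 2 may claim. A difference read as an intervention effect on PMTCT use could be partly a difference in case mix.

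**Working it through.** The plan gives no sample size, expected rate or power for PMTCT adherence, so there is no figure of its own to reproduce beyond the total of 6 sites x 65 = 390.

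**1. How many women contribute**
- Enrolled: 390 (Overview).
- Attrition: 10% (Power analysis).
- Women: half (Recruitment).
- Evaluable women: 390 x 0.9 / 2 = 175.5, about 176.
- Share conceiving: 20-40%, assumed. Per arm: 176 x 0.20 / 3 = 12 to 176 x 0.40 / 3 = 23.

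Precision for usual care against the pooled SCC arms, at 74% adherence and ignoring clustering:
- 12 vs 24 women: 1.96 x sqrt(0.74 x 0.26 x (1/12 + 1/24)) = 0.30.
- 23 vs 46 women: 1.96 x sqrt(0.74 x 0.26 x (1/23 + 1/46)) = 0.22.

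The 95% interval is therefore about ±22 to ±30 points.

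**2. Size of a purely selective difference**

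Assume PMTCT care is identical in all arms. Let s be the share of women not on ART. Adherence is assumed to be 80% if on ART and 50% if not; neither rate is in the documents.
- Usual care: 0.80(1 - s) + 0.50s = 0.80 - 0.30s.
- SCC, if a fraction d of women not on ART delay past follow-up: s' = s(1 - d) / (1 - sd), and adherence is 0.80 - 0.30s'.

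| ART coverage | Usual care | SCC, half delay | Difference | SCC, all delay | Difference |
|---|---|---|---|---|---|
| 70% | 71.0% | 74.7% | +3.7 | 80.0% | +9.0 |
| 80% | 74.0% | 76.7% | +2.7 | 80.0% | +6.0 |
| 95% | 78.5% | 79.2% | +0.7 | 80.0% | +1.5 |
| 100% | 80.0% | 80.0% | 0 | 80.0% | 0 |

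With 40% instead of 50% adherence off ART, and 25-100% delaying, the range is +2 to +12 points at 70-80% coverage and +0.5 to +2 at 95%.

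**3. Which coverage applies**

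Study Setting gives about 70-80% on ART, but for all 6000-8000 clients of a clinic. Trial clients are in serodiscordant relationships, and Research Participants says TASO provides ART to all such clients. The same paragraph says ART use is not an eligibility criterion and expects SCC to help clients start it. Coverage among enrolled women is therefore unknown, and the upper rows may be too pessimistic.

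**4. If selection acts only in SCC1**

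Pool SCC1 with an SCC2 arm in which nobody delays, each weighted by its number of pregnancies:
- 80% coverage, half delay: (0.90 x 0.767 + 1.00 x 0.74) / 1.90 = 0.753, or +1.3 points.
- 70% coverage, all delay: (0.70 x 0.80 + 1.00 x 0.71) / 1.70 = 0.747, or +3.7 points.

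**The case against.** **The bias may be negligible.** If nearly all enrolled women are on ART, the ART pathway yields about a point or nothing. This stands, and it means the documents do not establish that the contrast is materially biased. They establish only that it is unprotected.

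**Delay is not always selection.** A woman who starts ART and conceives later within follow-up is an intended benefit of SCC. This also stands: only deferral out of the denominator is selection, and complete deferral is an extreme case. The planned analysis cannot separate the two.

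**Covariates could deal with it.** ART use, CD4 and STIs are measured, and the covariates named for Aim 1 are only examples. In the model above, adjustment for baseline ART status would remove the illustrated bias. The plan does not name that covariate, however, and adjustment for it would not cover changed childbearing decisions or other routes into pregnancy.

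**The consequence is small.** The outcome is secondary, and a shift of a few points is far inside an interval of ±22 points or wider. That is fair, but it argues for description rather than a test.

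Three stronger readings are tempting but unsupported:
- A reader might infer that pregnancies of male clients' HIV-negative partners would be scored as non-adherent. Nothing says they are counted, and Follow-up sessions limits PMTCT to HIV-positive mothers. Naming female clients is a clarification only. That at most half the sample can contribute follows from the outcome itself and is not a bias.
- A reader might infer that this subset carries an intent-to-treat label. Data analysis attaches intent-to-treat to the primary analyses and completers to secondary analyses, so its reach to Aim 2 is unclear.
- A reader might infer that both SCC arms select equally. The explicit delay advice is SCC1 session content. SCC2 uses a simplified manual, and nothing shows the advice is in it.

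**Conclusion.** The point holds in a limited form. As planned, PMTCT adherence is compared within a post-randomisation subset that SCC is meant to shape, partly through a component of the endpoint. A difference between arms could therefore not be attributed to PMTCT care.

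The size is not derivable from the documents. On the assumed 80%/50% adherence rates it is +3 to +9 points at the clinic-wide ART coverage, about +1 point at 95% and zero at 100%. It is smaller in the pooled contrast if SCC2 does not select. The primary outcome is unaffected.

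**What to change.** In Aim 2, state that PMTCT adherence is reported among pregnant HIV-positive female clients and is descriptive. For each arm, give the number of women enrolled, the number pregnant, and the baseline ART status and CD4 of the pregnant women. If a model is fitted, include baseline ART status as a covariate. Make no efficacy claim from this subset.

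Do not replace the comparison with an all-women composite of being pregnant without full PMTCT. It counts conception against an arm: with 80% adherence in both, 40% vs 20% pregnant gives 0.40 x 0.20 = 8% vs 0.20 x 0.20 = 4% failure, so the arm that helped more women conceive looks worse.

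The cost is a few sentences in the analysis plan, using data already to be collected. The downside is that PMTCT adherence no longer supports a confirmatory claim between arms, which about 12-23 pregnant women per arm (assuming 20-40% conceive) could hardly support anyway.
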